Number of needed patients:

The number of needed patients was determined arbitrarily and is based on an estimated sufficient number to have a real incidence when means will be calculated.

→Number of patients in the cohort: 120

| | |
|-----------------------|---|
| Collected data | 
Preoperative phase:
 
Sociodemographic data: age, sex, weight, height
 
Medical & surgical history, risk factors and comorbidities
 
Primary diagnosis and operative indication.
 
Daily physical activities
 
Charnley Classification
 
Operative & immediate postoperative phases :
 
Perioperative & immediate postoperative complications;
 
Surgery description (assembly of components and sizes, description of the devices used in combination with Sagitta EVL-R stems);
 
Immediate postoperative radiologic evaluation;
 
Post-operative data (6 months, 1, 2, 5, and potentially between 5 to 8 years):
 
Radiologic evaluation (inclination of the cup, localization of the rotation center, presence of periprosthetic radiolucent line for the cup and the stem, height of the stem comparing with an anatomic locator)
 
Postoperative data through unique individual phone call corresponding to 5 to 8 postoperative years:
 
 - Oxford clinical scores - Daily physical activities - Global outcomes: Patient's satisfaction, walking ability, functional improvement, |
|-----------------------|---|

| | | | |
|---|--------------------------------|---|-------------------------------|
|  | Document No. 2019-10-EVLR-N | SAGITTA EVL-R STEMS – NOVAE / SAGITTA EVL-R CUPS | ID RCB : 2019-A01777-50 |
| | Version 02 | | Page No. Page 8 sur 28 |

release pain
- Charnley Classification

Postoperative complications all over the follow-up of patients between the preoperative period until the phone call (5 to 8 years)

| | | | |
|--|----------------------------------|---|---|
|  serf | Document No. | SAGITTA EVL-R STEMS – NOVAE / SAGITTA EVL-R CUPS | ID RCB : 2019-A01777-50 |
| | 2019-10-EVLR-N Version 02 | | |
| | | | Page No. Page 9 sur 28 |

ABBREVIATIONS

| | |
|-------------|---|
| AAOS | American Academy of Orthopaedic Surgeons |
| ADE | Adverse device Effect |
| AE | Adverse Event |
| BMI | Body Mass Index |
| CRF | Case Report Form |
| HAS | Haute Autorité de Santé |
| HHS | Harris Hip Score |
| NICE | National Clinical Guideline Centre |
| OHS | Oxford Hip Score |
| SAE | Serious Adverse Event |

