- As well as the face femur picture, the profile view of the femur would inform (in another dimension) about a potential subsidence / or a radiolucent line confirming a radiological and/or a clinical loosening of stem, that can lead to a surgical revision.
- The face radiography of the cotyle will mainly measured the inclination of the implant and its stability over time through its migration. The radiolucent line will be appreciated (De LEE and Charnley scales) to emphasize of potential radiological level of loosening. This finding may have no clinical impact on the patient daily life. It will depend of the level of loosening of the cup and its evolution.

The daily physical activity will be harvested postoperatively to see the incidence of the reparation of the patient daily autonomy at their last timepoints.

The co-morbidity will be measured preoperatively and postoperatively using the Charnley classification. The goal is to estimate if the co-morbidity may be detrimental to the clinical results and their evolution and potentially to identify the nature of detrimental factors.

All complications will be recorded during the study. A global survival rate would therefore be calculated at each timepoints. As the same manner, an aseptic loosening rate and a global complication rate will be evaluated. Other specific complication rate would be evaluated is considered representative and pertinent.

The global satisfaction of patients will be measured at the last postoperative timepoints.

The walking ability will be measured at the last postoperative timepoints.

The global functional improvement will be measured at the last postoperative timepoints.

The pain release will be estimated at the last postoperative timepoints.

The length of the operated limb will be harvested to see if the chosen assembly was adequate and to see its evolution over time.

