6.4 Secondary endpoints

The endpoints are:

- The functional improvement following a total hip arthroplasty will be evaluated postoperatively at the

| | | |
|---|---|---------------------------------------|
|  Document No. 2019-10-EVLR-N | SAGITTA EVL-R STEMS – NOVAE / SAGITTA EVL-R CUPS | ID RCB : 2019-A01777-50 |
| | Version 02 | Page No. Page 17 sur 28 |

last follow -up between 5 and 8 years postoperative years through the validated Oxford Hip Score

- The daily physical activity will be appreciated postoperatively at the last follow-up postoperatively.
- The co-morbidity will be measured preoperatively and postoperatively at 6 months, 1, 2, 5, and potentially between 5 to 8 years postoperatively.
- The global satisfaction of patients will be measured at the last follow -up between 5 and 8 years postoperative years.
- The walking ability will be measured at the last follow-up between 5 and 8 years postoperative years.
- The global functional improvement will be measured at the last follow-up between 5 and 8 years postoperatively.
- The pain release will be estimated at the last follow-up between 5 and 8 years postoperatively.
- The length of the operated limb will be harvested at 6 months, 1, 2, 5 and/or at 5 to 8 years postoperatively, if available.
- Adverse events all along the postoperative follow-up and if the information is available in patients' files:
 - Nature and origins of complications.
 - graded as serious (leading to death, life-threatening condition, requiring hospitalization or lengthening of hospital stay, leading to permanent or significant disability);
 - or graded as not serious and as implant-related (migration, subsidence) or surgery-related (iatrogenic event) or other relationships (i.e. aseptic loosening...), idiopathic events, possible related pathology events, but not limited to.

6.5 Secondary radiographic outcomes:

Postoperative Radiological assessments will be followed at immediate postoperative period and at 6 months, 1, 2, 5, and potentially between 5 to 8 years postoperatively. The inclination of the cup, the localization of the center of rotation, and the presence or not of a periprosthetic radiolucent line will be followed and its location. Moreover, the distance, the height of the stem comparing with an anatomic locator (greater or lesser trochanter) and the presence or not of a periprosthetic radiolucent line all around and its location.

7 Study design

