8.5 Exclusion criteria

After inclusion, patients can be excluded from the study if the final follow up is 24 months and if available data at the 24 months postoperative visit is too poor.

9 Study procedures

Patient information:

This observational study does not require any additional eligibility criteria, any additional exam. According to French regulation, each patient is appropriately informed of his/her freedom to decline or agree to participate to the study (thanks to the information note) and of his rights regarding medical data collection.

Study withdrawal:

Patients may withdraw from the study at any time at their own request, or they may be withdrawn at any time at the discretion of the investigator or sponsor for safety, behavioral, or administrative reasons. In any circumstance, every effort should be made to document patient outcome, if possible.

| | | | | | |
|--|----------------|---|-------------------------|----------------|--|
|  serf | Document No. | SAGITTA EVL-R STEMS – NOVAE / SAGITTA EVL-R CUPS | ID RCB : 2019-A01777-50 | | |
| | 2019-10-EVLR-N | | Page No. | Page 19 sur 28 | |

10 Collected data

Patients will be followed at 2 stages: in their medical history files and through a phone call [after](#) the surgery.

| Endpoints | Preoperative | Per-operative | Immediate post-operative | Visit 6 months | Visit 1 year | Visit 2 years | Last visit over 2 years | Phone call to patients |
|--|---|---------------|--------------------------|----------------|--------------|---------------|-------------------------|------------------------|
| Patient information (gender, age, weight, height) | X | | | | | | | |
| Eligibility criteria | X | | | | | | | |
| Medical & surgical history | X | | | | | | | |
| Oxford questionnaires | | | | | | | | X |
| Daily physical activity | | | | | | | | X |
| Charnley Classification | X | | | X | X | X | X | X |
| Surgery - Assembly components description | | X | | | | | | |
| Peroperative Incidents | | X | | | | | | |
| Global results: Patient satisfaction Walking ability Functional improvement Pain release | | | | | | | | X |
| Length of the operated limb | | | | | | | | X |
| Radiologic assessment | Inclinaison of the Cup and localization of the center of rotation | | X | X | X | X | X | X |
| | Periprosthetic radiolucent line - Cup | | X | X | X | X | X | X |
| | Stem height/ anatomic locator | | X | X | X | X | X | X |
| | Periprosthetic radiolucent line - stem | | X | X | X | X | X | X |

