10.4 Postoperative phases at 6 months, 1, 2, 5 to 8 years

Daily physical activity: this parameter is graded as:

- Bedridden
- Sedentary
- Semi sedentary
- Light activity
- Moderate activity
- Heavy activity

Classification of Charnley – Adversely impacting outcomes factors: this classification is graded as 3 levels (A: none factor, B: damage of the contralateral hip, C: Other associated morbidities interfering on the walking ability).

The global results of the surgery - through the global satisfaction of patients, the potential improvement of the walking ability, the functional improvement and the pain release; using closed-questions.

| | | | |
|--|------------------------------|---|-------------------------|
|  serf | Document No. | SAGITTA EVL-R STEMS – NOVAE / SAGITTA EVL-R CUPS | ID RCB : 2019-A01777-50 |
| | 2019-10-EVLR-N Version 02 | | |

Radiological evaluation:

The inclination of the cup, the localization of the center of rotation, and the presence or not of a periprosthetic radiolucent lines will be followed and their potential locations. Moreover, the distance, the height of the stem comparing with an anatomic locator (greater or lesser trochanter) and the presence or not of a periprosthetic radiolucent line all around and its location. Qualitative migration and subsidence of the implant are also deduced indirectly.

Postoperative Complications

Complications will be recorded as soon as there will be encountered in patients' files. All data will be recorded if available? Analysis of these events will be analyzed jointly with the investigator. In retrospective manner, No relevant events in nature or incidences will be declared following the procedure in the following section, if applicable. The investigator should investigate the occurrence of adverse events.

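### The endpoints set 5 years as a distinct time point for radiographs and Charnley class, but Table 1 has no 5-year column and section 10.4 gives a third schedule

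*Protocol*

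**What the plan says.** **Endpoints.** Section 6.5 of the protocol states: "Postoperative Radiological assessments will be followed at immediate postoperative period and at 6 months, 1, 2, 5, and potentially between 5 to 8 years postoperatively". Section 6.4 sets the same points for co-morbidity: "The co-morbidity will be measured preoperatively and postoperatively at 6 months, 1, 2, 5, and potentially between 5 to 8 years postoperatively". Section 6.2 says that co-morbidity is measured with the Charnley classification. The Summary repeats both schedules under its secondary endpoints. Under its collected data, where radiology is listed, it again gives "Post-operative data (6 months, 1, 2, 5, and potentially between 5 to 8 years". In all of these, 5 years stands apart from the optional 5-to-8-year point.

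**Collection table.** The postoperative columns of Table 1 (section 10) are immediate, 6 months, 1 year, 2 years, "Last visit over 2 years" and the phone call to patients. The Charnley row reads "Charnley Classification | X | | | X | X | X | X | X", so it is marked before surgery, at 6 months, 1 and 2 years, at the last visit and at the phone call.

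**Section 10.4.** Its heading is "Postoperative phases at 6 months, 1, 2, 5 to 8 years", which merges 5 years and 5 to 8 years into one phase.

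**Complications and survival.** Section 6.2 says: "A global survival rate would therefore be calculated at each timepoints". The Summary collects "Postoperative complications all over the follow-up of patients between the preoperative period until the phone call (5 to 8 years".

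**The concern.** One protocol gives three late schedules for the same measurements. This matters because the files are read once, over 8 to 10 days (Summary; section 14.2), and the abstractor needs to know which films to measure. A later analysis plan cannot recover a 5-year film that nobody measured.

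The radiographic variables (cup inclination, centre of rotation, stem height, radiolucent lines) and Charnley class are planned as values at set time points. Section 13.2 reports frequencies and percentages and compares them with the literature. A percentage from a column of unstated timing cannot be labelled a 5-year result, and it cannot be matched to a published rate at a known time. Section 6.2 also wants subsidence followed from the immediate film to the middle and long term, and a single late column of mixed timing cannot separate those two periods.

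**Working it through.** The protocol gives no numerical figure to reproduce on this point. The check compares the schedules and then works out how wide the late column can be.

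**Step 1: schedules side by side.**

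| Place | 6 months, 1 and 2 years | 5 years | Later |
|---|---|---|---|
| Summary and 6.5 (radiographs) | yes | yes, separate | 5 to 8 years, optional |
| Summary and 6.4 (co-morbidity, Charnley) | yes | yes, separate | 5 to 8 years, optional |
| 10.4 heading | yes | merged with later | 5 to 8 years, one phase |
| Table 1, file-based columns | yes | none | last visit, any time after 2 years |
| Table 1, phone call | – | none | 5 to 8 years |

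The 5-year point is the one with no matching column in Table 1. For Charnley class, the phone call covers 5 to 8 years but not 5 years specifically. For radiographs, the file is the only possible source. As extracted, the radiology rows carry a mark under the phone call. Merged cells make that alignment unreliable, so nothing here rests on it. No column heading in Table 1 names 5 years, however the marks fall.

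**Step 2: what the late column can span.** Inputs: surgery between 2011 and 2014 (Summary), estimated end of follow-up in November 2019 (section 7.3), minimum follow-up of 24 months (section 8.2). Elapsed years = days from surgery to collection / 365.25.

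- Earliest surgery: 1 January 2011 to 30 November 2019 is 3,255 days; 3,255 / 365.25 = 8.91 years (8.83 if collection is on 1 November).
- Latest surgery: 31 December 2014 to 1 November 2019 is 1,766 days; 1,766 / 365.25 = 4.84 years (4.91 if collection is on 30 November).

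The column can therefore hold a visit from just over 2 to about 8.9 years, a width of about 8.9 − 2 = 6.9 years. If the 8-year maximum stated in the Summary is applied, the width is 8 − 2 = 6 years.

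**Step 3: what happens to individual patients if Table 1 is followed literally.** A patient with films at 5 and 7 years enters the 7-year film and the 5-year film has no place. A patient last seen at 2.5 years enters that film in the same column.

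**Step 4: timing information.** Section 12.3 lists the intervention date among the recorded data. The data lists in sections 10 and 12.3 name no date for file visits or films, so they do not by themselves let the late column be re-sorted by follow-up time.

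**The case against.** The strongest case on the other side has four parts.

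- **Survival does not need a visit column.** A reader might infer that 5-year survival is also lost. The documents do not support that. No 5-year survival result is named, section 6.4 does not list survival as an endpoint, complications are collected through to the phone call, and the intervention date is held. Survival needs event dates, not a 5-year column. This part stands in full.
- **Loss or pooling is not certain.** The Summary still lists 5-year radiology for collection, and the case report form (appendix 19.6), which may fix the fields, is not shown. This stands too. The point is a contradiction whose consequence follows only if Table 1 governs. Visit windows, film dates and denominators may be set in the form or an analysis plan, so their absence is not held against the protocol.
- **Table 1 has two late columns, not one.** The phone call gives Charnley class and complications at 5 to 8 years. That is right, and it leaves radiographs as the main casualty.
- **An open last-visit column is defensible.** Section 9 requires no additional exam, so a 5-year film may not exist, and patients last seen between 2 and 5 years are eligible and need a place. That is a good reason to keep the column. It does not reconcile Table 1 with endpoints that name 5 years.

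**Conclusion.** The point holds as an internal contradiction: wrong as written, for secondary endpoints only. The Summary and sections 6.4 and 6.5 require radiographs and Charnley class at 5 years, Table 1 offers no column for it, and section 10.4 words the schedule a third way. The primary endpoint, the Oxford Hip Score by phone, is unaffected.

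The size is the width of the late column: just over 2 to about 8.9 years, or to 8 years if the Summary's maximum is enforced. This assumes surgery at any date from the start of 2011 to the end of 2014, collection in November 2019, and abstraction that follows Table 1.

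A reader might go further and infer that late loosening will be understated by a given amount. The documents do not support that. They give neither the distribution of last-visit times nor expected radiographic rates, so neither the direction nor the size of any distortion can be stated.

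**What to change.** 1. Add a 5-year column with a stated window to Table 1. In setting the window, note that patients operated in December 2014 will not have reached 5 years by November 2019.
2. Keep the existing last-visit column, so that eligible patients last seen between 2 and 5 years are still captured. Replacing it with 5-year and 5-to-8-year columns would leave them without a place.
3. Record the date of every file visit and film.
4. Report each time point with its number of patients available, and report the last visit with its actual follow-up time.
5. Use one schedule in the Summary, 6.4, 6.5, 10.4 and Table 1.

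The cost is one extra column, a date field per visit and film, and measurement of any 5-year film found, all while the files are already open. No extra patient contact or examination is needed.

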10.1 Preoperative phase

During the ~~first visit~~-selection phase, the principal investigator records patient data and checks eligibility criteria (inclusion and non-inclusion criteria).

Then, the data collected are:

Sociodemographic data:

- Age, sex, weight, height,

Medical history:

- Primary diagnosis and operative indication.
- Co-morbidities and risk factors: alcoholism, Overweight, anticoagulant intake, cardiovascular, Sagitta EVL-R tension, diabetes, thromboembolic history, Rheumatoid arthritis, Osteoporosis, Musculoskeletal comorbidity, other (to be defined)

Daily physical activity: these parameters is graded as:

- Bedridden
- Sedentary
- Semi sedentary
- Light activity
- Moderate activity
- Heavy activity

Classification of Charnley – Adversely impacting outcomes factors: this classification is graded as 3 levels (A: none factor, B: damage of the contralateral hip, C).

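### Daily physical activity is listed before surgery in section 10.1 and the Summary, but Table 1 and the endpoint leave that baseline out, so change in daily autonomy is not assured

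*Protocol*

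**What the plan says.** The protocol gives several collection schedules for the same six-grade scale, which runs from bedridden to heavy activity.

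- Section 10.1, on the preoperative phase, includes it: "Daily physical activity: these parameters is graded as". The Summary's list of preoperative data does so too: "Daily physical activities Charnley Classification". The Summary lists it again under the phone call.
- Section 10.4, whose heading covers 6 months, 1, 2 and 5 to 8 years, includes it as well: "Daily physical activity: this parameter is graded as".
- Table 1 in section 10 has one mark, in the phone-call column: "Daily physical activity | | | | | | | | X".
- The objective in section 6.2 reads: "The daily physical activity will be harvested postoperatively to see the incidence of the reparation of the patient daily autonomy at their last timepoints".
- The endpoint in section 6.4 reads: "The daily physical activity will be appreciated postoperatively at the last follow-up postoperatively".

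The global results (satisfaction, walking ability, function, pain) show part of the same pattern. Section 10.4 lists them under its combined heading, including "the potential improvement of the walking ability, the functional improvement and the pain release; using closed-questions". Table 1 and the Summary place them at the phone call only, and section 6.4 at the last follow-up only.

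**The concern.** The objective asks what the repair does for the patient's autonomy. One grade recorded 5 to 8 years after surgery shows how active the patient is then, not whether that is better or worse than before. The cohort mixes primary arthrosis, fractures and revisions, so starting levels are likely to differ widely, and the late grade alone is hard to read as an effect of the operation.

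The baseline matters more here because little else can stand in for it. The Oxford Hip Score is taken only at the phone call, and the global items ask about improvement in hindsight without a recorded starting point. Activity is the only graded functional scale that the protocol lists on both sides of the operation.

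The timing matters too. Data are to be harvested once, over 8 to 10 days (Summary and section 14.2), into a spreadsheet of the data the protocol requires (section 12.1). If that spreadsheet is laid out from Table 1, the preoperative grade is not extracted, and recovering it means reopening the files. An analysis plan written later cannot restore a field that was never collected.

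**Working it through.** No formula applies. The sample size of 120 is stated to be arbitrary, so there is no design figure to reproduce. The check sets the places side by side.

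| Place in protocol | Preoperative | 6 months, 1 and 2 years | Phone call or last follow-up |
|---|---|---|---|
| Summary, collected data | yes | no | yes |
| Section 10.1 | yes | not covered | not covered |
| Section 10.4 | not covered | yes | yes |
| Table 1 | no | no | yes |
| Objective, section 6.2 | no | no | yes |
| Endpoint, section 6.4 | no | no | yes |

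**Is the empty preoperative cell an artefact of reading the PDF?** This is unlikely. The Charnley row of the same table reads "Charnley Classification | X | | | X | X | X | X | X". Its eight cells fall under the eight column headings, with marks at the preoperative phase, the four visits and the phone call. The activity row also has eight cells, and only the last is filled.

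**Which entry is the outlier at the intermediate visits?** For 6 months to 8 years the Summary lists radiologic evaluation only, and it puts activity and the global results at the phone call, as Table 1 does. Section 10.4 therefore stands alone there. No endpoint in section 6.4 uses intermediate-visit activity or intermediate-visit global results.

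**Which entry is the outlier before surgery?** Here the Summary and section 10.1 agree with each other and disagree with Table 1.

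**What can be analysed under each reading?**
- If Table 1 governs the database, 0 of 120 patients have a before/after pair of activity grades.
- If section 10.1 and the Summary govern, the number of pairs is the number of patients reached by phone whose file also holds a preoperative grade. The ceiling is 120. The protocol gives no basis for a closer figure.
- Under either reading, the endpoint as worded in section 6.4 does not use the baseline.

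**The case against.** The strongest reply is that the objective, the endpoint and Table 1 agree with one another: activity is a late-status measure. The planned analysis in section 13.2 is descriptive, and a preoperative grade kept as a cohort descriptor would not contradict a postoperative status endpoint. On that view, reporting change is a suggestion and not the correction of an error. This stands in part. The schedule conflict has to be reconciled in any case. The case for a shift table rests on the objective's reference to what the repair does for autonomy, which a status measure answers poorly.

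A reader might infer more than the documents support:

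- *That the change in activity cannot be measured at all, or that no patient will have a pair.* This follows only if Table 1 overrides section 10.1 and the Summary. Nothing in the protocol gives it that precedence, and the CRF listed as appendix 19.6 is not available to settle the matter.
- *That the study would have no within-patient change of any kind.* It would have some. Charnley class is recorded before surgery and repeatedly after it, stem height and cup position are followed from the immediate postoperative period, and the global items ask patients about improvement. What would be missing is a graded functional scale with a recorded baseline.
- *That adding the baseline would isolate the effect of surgery.* It would not, because there is no control group. For fracture patients the protocol also does not say whether preoperative means before the injury or on admission, and the two readings could push the shift in opposite directions.

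It is also fair to say that Table 1 is loose elsewhere. Limb length is planned at several visits in section 6.4 but marked only at the phone call. That makes a drafting slip more likely than a decision to drop the baseline.

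**Conclusion.** The point holds as a schedule conflict with a consequence for one secondary endpoint. Daily physical activity is planned before surgery in two places and left out of the schedule table and the endpoint. A database that follows Table 1 would lose the baseline, and the endpoint as defined reports late status where the objective asks about the effect of the repair.

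The loss is conditional. It is complete if Table 1 governs. If section 10.1 governs, a pre-post change can be computed for an unknown part of the 120 patients. This assumes that at least some 2011-2014 files allow a six-level preoperative grade to be assigned, which the protocol does not show. The primary endpoint is not affected. The point is worth settling before the single data harvest.

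**What to change.** 1. In Table 1, add the preoperative mark for daily physical activity, to agree with section 10.1 and the Summary.
2. In section 6.4 and the Summary, keep the grade at last follow-up and report beside it the shift from preoperative to phone call: improved, same or worse, each with a 95% CI.
3. Split the shift table by indication: fracture, other primary, revision. State whether preoperative means before or after the injury for fracture patients.
4. Give the number of patients with a recorded baseline grade, and describe the result as an uncontrolled pre-post change.
5. Reconcile section 10.4 with Table 1 and the Summary in the same way for activity and for the global results: phone call only, since no endpoint uses the intermediate visits.

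This is a cheap improvement: one table cell, a sentence or two in the endpoint, a wording change in section 10.4 and one cross-tabulation per indication group. It needs no extra examination or visit. The downside is that some 2011-2014 files may lack the preoperative grade, so the shift table may cover only part of the cohort, and the indication groups will be smaller still.
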